3.6.2.2. Serious Adverse Events

A “SAE” is any AE that:

- Results in death;
- Is life-threatening (Note: the term “life-threatening” refers to any AE that, as it occurs, puts the subject at immediate risk of death. It does not refer to an AE that hypothetically might have caused death if it were more severe).

- Results in hospitalization or prolongation of current hospitalization (not including hospitalization for a pre-existing condition that has not increased in severity or frequency from the subject's underlying medical condition prior to entry into the study).
- Is a congenital anomaly/birth defect in the offspring of a subject.
- Is another serious (important medical events) event.
- Results in persistent or significant disability/incapacity.

(Note: Important medical events may not be immediately life-threatening or result in death or hospitalization but may be considered serious when, based on the appropriate medical judgment, they may jeopardize the subject or require medical or surgical intervention to prevent one of the outcomes listed above. Examples of such medical events include allergic bronchospasm requiring intensive treatment in an emergency room or at home; blood dyscrasias or convulsions that do not result in inpatient hospitalization; or development of drug dependency or drug abuse.)

3.6.2.3. Severity of Adverse Events

The Investigator is to classify the severity (intensity) of an AE according to the following definitions:

- Mild – The subject was aware of the signs and symptoms, but the signs and symptoms were easily tolerated and do not interfere with daily activity.
- Moderate – The signs and symptoms were sufficient to restrict, but did not prevent, usual daily activity for the subject. The subject is still able to function.
- Severe – The subject was unable to perform usual daily activity.

The maximum intensity of an AE (mild, moderate, or severe) will be assessed taking into account the possible range of intensity of the symptom(s).

3.6.2.4. Relationship of Adverse Events to Study Treatments

The Investigator is responsible to assess the relationship of an AE to the IP treatment using good clinical judgment and definitions outlined in [Table 5](#).

Table 5: Relationship of AE to Study Drug

Association	Definition
Not related	The AE is clearly explained by another cause not related to the IP administration; the temporal relationship of the AE to IP administration makes a causal relationship unlikely, or, concomitant medication, therapeutics interventions, or underlying condition provide a sufficient explanation for the observed AE
Possibly Related	The AE and administration of IP are temporally related, but the AE can be explained equally well by causes other than the IP administration
Probably Related	The AE and use of IP are temporally related, and the AE is more likely explained by IP administration than by other causes
Definitely Related	The AE and IP administration are related in time, and a direct association can be demonstrated. Concomitant medication, therapeutics interventions, or underlying conditions do not provide a sufficient explanation for the observed AE

3.6.3. Reporting Adverse Events

Adverse events that occur from the time of informed consent through completion of the last study visit should be reported.

Every attempt should be made to describe the AE in terms of a diagnosis. If a clear diagnosis has been made, individual signs and symptoms will not be recorded unless they represent atypical or extreme manifestations of the diagnosis, in which case they should be reported as separate events. If a clear diagnosis cannot be established, each sign and symptom must be recorded individually.

Any SAEs occurring in a subject receiving study drug must be reported to the Sponsor within 24 hours of the site being informed of the event, even if the event does not appear to be drug-related. The report must be made by sending a completed SAE Report form to the Sponsor. Any pertinent follow-up information should be provided in a similar manner. Contact information is provided in [Section 3.7.1](#).

3.6.4. Adverse Event Follow-up

Any ongoing AE at the time of study completion or withdrawal will be followed until the AE is resolved or the subject is referred to his/her own PMD. The Investigator and the Sponsor will decide if longer follow-up is appropriate on a case-by-case basis. Subjects who experience any clinically significant AE will remain under medical supervision until the Investigator or the Sponsor's Medical Monitor deems the AE to be resolved, stabilized, or no longer serious enough to warrant follow-up.

3.6.5. Pregnancy reporting

Prior to study enrollment, females of childbearing potential must be advised of the importance of avoiding pregnancy during study participation and the potential risk factors for an unintentional pregnancy.

A UPT will be performed on all females of childbearing potential at Day 1 (day of first patch application) and EOS. All women of childbearing potential will receive a UPT prior to the first study drug administration and the study drug must be withheld until the results of laboratory pregnancy testing are available. If pregnancy is confirmed, the subject must not receive any study drug and must not be enrolled in the study.

Pregnancy follow-up should be reported to the IRB within 24 hours of first knowledge on a Pregnancy Report Form. Follow up will describe the outcome of the pregnancy, including any voluntary or spontaneous termination, details of the birth, and the presence or absence of any congenital abnormalities or birth defects.

3.6.6. Expected Adverse Events

Any observed response in the patch test area that can be denoted using the irritation criteria summarized in [Table 3](#) and [Table 4](#) will not be considered an AE.

Tape related reactions will only be recorded as AEs when the subject is discontinued due to tape reaction.

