At the end of the Induction Phase, the subjects will enter a Rest Period of 10-17 days and then a Challenge Phase. One application/irradiation session may be missed during the Induction Phase. If a subject misses an irradiation session during the Induction Phase, an additional application/irradiation session will be scheduled the Monday of rest period (week 4).

At Challenge, each study product will be applied in an amount of 0.2 g to 2 naive sites once for approximately 24 hours (\pm 4 hours) under semi-occlusive patches. After 24 hours (\pm 4 hour) of product application, all sites will be evaluated, and one application site of each product and the additional untreated site will be irradiated. The sites will be examined for dermal reactions at approximately 24 hours (\pm 4 hours), 48 hours (\pm 4 hours), and 72 hours (\pm 4 hours) post-irradiation. A Rechallenge should be performed if a cutaneous response observed during the Challenge Phase indicates possible photosensitization or at the discretion of the Investigator.

The safety endpoints for this study are irritation responses during the Induction Phase, positive responses at Challenge (ie, reactions indicative of a sensitization response) and AEs.

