3.3.3. Interruption or Discontinuation of Treatment

A reaction of at least moderate erythema (2) accompanied with mild, but definite edema (1) to a study product observed after the first patch application/irradiation sequence of the Induction Phase may indicate the subject to be pre-sensitized and may cause the discontinuation of the subject from the study.

After the second reading of the Induction Phase, either of the following conditions will require that the study product be applied to a naïve patch site under open patch conditions:

- Reaction of >50% “p” or “p” with no erythema, mild but definite erythema, moderate or severe erythema; or “D” (see [Table 3](#) and [Table 4](#));
- Any reaction of definite erythema (mild, moderate or severe) with definite edema.

Study product may not be relocated more than twice.

If the reactions noted above occur on an irradiation day during the Induction Phase, the sites will not be able to be irradiated. Patches will be relocated at the subject’s next visit.

The 3 weeks of continuous patch contact during the Induction Phase frequently results in tape-related irritation that is exacerbated by warm weather, but which occurs among some individuals irrespective of the season. Tape-related irritation will not be graded as a photosensitivity response at the patch site but will be noted separately on the case report form (CRF). Severe tape-related irritation will necessitate a change in the application site. As above, the application site will only be changed twice and then the subject must be discontinued.

One application/irradiation session may be missed during the Induction Phase. In case of a missed application/irradiation, an additional application/irradiation during Week 4 must be

performed. In this case, no evaluation will be required following irradiation. Only one missed patch application or irradiation is allowed. A subject must be discontinued and considered not complete if more than one application or irradiation is missed.

In accordance with legal requirements and ICH-GCP guidelines, every subject has the right to refuse further participation in the study at any time and without providing reasons (see also [Section 5.3](#)). A subject's participation is to be terminated immediately upon his/her request. The Investigator should seek to obtain the reason and record this on the CRF.

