3.6. Adverse Events

3.6.1. Method of Determining Adverse Events

Safety assessments will include recording AEs reported spontaneously by the subject or collected by the Investigator. Adverse events will be collected during the period from the time of the signature of the informed consent form and first trial-related activity performed until the end of the trial. Adverse events will be recorded at each visit throughout the study on the appropriate CRF. Every attempt should be made to describe the AE in terms of a diagnosis. If a clear diagnosis has been made, individual signs and symptoms will not be recorded unless they represent atypical or extreme manifestations of the diagnosis, in which case they should be reported as separate events.

Subjects should be asked whether, since the time of the last observation or visit, they had any of the following:

- Experience any changes in well-being;
- Used any new medications other than those permitted in the inclusion criteria;
- Changed medication regimens (both prescription and OTC); and/or
- Were admitted to a hospital or had any accidents.

All questions should be of a general nature and should not suggest symptoms.

When an AE is suspected, all relevant evaluations will be carried out and appropriate treatment provided. Additional follow-up will be done as necessary ([Section 3.6.4](#)) and recorded in the subject's source documents, and the results will be provided to the Sponsor.

For AE definitions and reporting requirements refer to [Section 3.6.2](#) and [Section 3.6.3](#).

Note: Any observed response which can be denoted using the irritation criteria summarized in [Table 3](#) and [Table 4](#) will not be considered an AE. Likewise, any tape-related irritation will only be noted as an AE when all patches are discontinued due to tape reaction around all sites (see [Section 3.6.6](#)).

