3.6.2. Adverse Event Definitions

3.6.2.1. Adverse Events

Information about all local and systemic AEs, whether volunteered by the subject, discovered by Investigator questioning, or detected through other means, will be collected and recorded on the AE CRF and followed as appropriate.

An AE is defined as any untoward medical occurrence in a patient or clinical investigation subject administered a pharmaceutical product (or cosmetic product), which does not necessarily have a causal relationship with this treatment. An AE can therefore, be any unfavorable and unintended sign, symptom, or disease temporally associated with the use of a medicinal IP, whether or not considered related to the medicinal IP.

Any AE that is considered related to the IP must be followed by the investigator until it is resolved or until the medical condition of the subject is stable; all relevant follow-up information will be reported to MC2 or designee. Adverse Events will be coded using the Medical Dictionary for Regulatory Activities (MedDRA).

Medical conditions/diseases present before starting study treatment are considered AEs only if they worsen after starting study treatment (any study procedures specified in the protocol). Any AEs occurring before starting study treatment but after signing the ICF are recorded on the Medical History/Current Medical Conditions CRF.

To the extent possible, each AE will also be described by:

1. its duration (start and end dates),
2. the severity grade (mild, moderate, severe)
3. its relationship to the study drug,
4. the action(s) taken, and
5. as relevant, the outcome.

Note: Any observed response which can be denoted using the irritation criteria summarized in [Table 3](#) and [Table 4](#) will not be considered an AE. Likewise, any tape-related irritation will not be noted as an AE.

The outcome of an AE will be classified as recovered, recovered with sequelae, recovering/resolving, ongoing, or death.

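### A product-site reaction that stops a subject after the first Induction sequence cannot be an AE, and its scores appear in no specified Induction display (minor)

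*Protocol*

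**What the plan says.** **AE rule.** Protocol 3.6.6 takes "Any observed response in the patch test area that can be denoted using the irritation criteria summarized in" Tables 3 and 4 and rules that it is not an AE. Sections 3.6.1 and 3.6.2.1 repeat the rule. None of the three makes an exception for a response that ends a subject's participation. Tape reactions are treated differently. Under 3.6.6, "Tape related reactions will only be recorded as AEs when the subject is discontinued due to tape reaction"; under 3.6.1, "any tape-related irritation will only be noted as an AE when all patches are discontinued due to tape reaction around all sites". Section 3.6.2.1 disagrees with both: "Likewise, any tape-related irritation will not be noted as an AE".

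**Stopping rule.** Under Protocol 3.3.3, a product reaction of at least moderate erythema (2) with mild edema (1) after the first Induction sequence "may indicate the subject to be pre-sensitized and may cause the discontinuation of the subject from the study". Relocation to a fresh site comes later: "After the second reading of the Induction Phase, either of the following conditions will require" it.

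**Endpoints and displays.** Protocol 3.1 states: "The safety endpoints for this study are irritation responses during the Induction Phase, positive responses at Challenge", and adds AEs as the third. Protocol 4.6.1 and SAP 11.7 say that all assigned scores will be summarized by treatment and time point, and name no population. The SAP shells are narrower. Tables 14.2.1.1 and 14.2.1.2 (both parts) and Listing 16.2.6.1 are headed Population II, which SAP 11.2.2 limits to subjects with 6 applications and at least 11 readings in Induction. Listing 16.2.6.3 is headed all randomized subjects but covers Challenge only.

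**The concern.** Keeping routine scored responses out of the AE data is sound, because they are a safety endpoint in their own right and are tabulated as scores. That reasoning fails when the scores are not tabulated either. Here the subject leaves the irritation displays because of the very reaction those displays measure, and the AE displays cannot take it up.

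Induction irritation and AEs are two of the three named safety endpoints, and this reaction would count under neither. Table 14.3.1.1 would show no treatment-related TEAE, and no TEAE leading to discontinuation, for a withdrawal that the product caused. The Induction frequencies would come from completers alone, with nothing to tell the reader that a strong early reactor had been set aside.

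There is also a point of subject care. A final evaluation is attempted for anyone who withdraws, but follow-up to resolution (Protocol 3.3.3, 3.3.4 and 3.6.4) and prompt reporting of an unusual frequency of events (3.7.2) are both worded for AEs.

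**Working it through.** **1. Reproduce the plan's figure of 11 readings.** From Protocol Table 2, the Induction readings after first application fall on:

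- Tuesdays: Days 2, 9, 16
- Thursdays: Days 4, 11, 18
- Fridays: Days 5, 12, 19
- Mondays: Days 8, 15

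That is 3 + 3 + 3 + 2 = 11, which matches the minimum in Protocol 4.3 and SAP 11.2.2. Applications fall on Days 1, 4, 8, 11, 15 and 18, which is 6. The minimum number of readings equals the number scheduled.

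**2. Apply the Population II rule to the stopped subject.** After the first sequence there has been 1 application (Day 1) and 1 reading (Day 2) or 2 readings (Days 2 and 4). The shortfall is 6 − 1 = 5 applications and at least 11 − 2 = 9 readings. The subject leaves the study, so this holds for both products.

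**3. Look for the reaction in each specified output.**

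| Output | Population | Shows this reaction? |
|---|---|---|
| Tables 14.2.1.1 and 14.2.1.2, Listing 16.2.6.1 | II | No, subject is outside II |
| Listing 16.2.6.2 | Not stated | No, subject has no relocated site |
| Listing 16.2.6.3 | All randomized | No, Challenge only |
| Tables 14.2.1.3 and 14.2.1.4 | I | No Induction scores; a row counts subjects classed as sensitized |
| Table 14.3.1.1, Listing 16.2.7.1 | III | No, barred from being an AE |
| Tables 14.1.1 and 14.1.3, Listing 16.2.1 | All randomized (14.1.1 also counts those screened) | Withdrawal or attendance only, no scores |
| Listing 16.2.9 | All randomized | Possibly, as free text |

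The trigger is stated in Table 3 grades, so the reaction is always scorable and the AE exclusion always applies. None of the 9 withdrawal reasons in Protocol 3.3.4 names a site reaction that is not an AE. It would be filed under investigator judgment or other.

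**4. Size.** The documents give no expected number, k. The following is illustration only, assuming 50 completers, no other dropouts and no such reaction among the completers. The share of treated subjects is k/(50 + k), with exact 95% intervals.

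| Assumed k | Displays as specified | All treated subjects |
|---|---|---|
| 0 | 0/50 (0 to 7.1%) | 0/50 (0 to 7.1%) |
| 1 | 0/50 (0 to 7.1%) | 1/51 = 2.0% (0.0 to 10.4%) |
| 2 | 0/50 (0 to 7.1%) | 2/52 = 3.8% (0.5 to 13.2%) |
| 3 | 0/50 (0 to 7.1%) | 3/53 = 5.7% (1.2 to 15.7%) |

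Other dropouts enlarge the denominator and lower these shares.

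**The case against.** **The exclusion is deliberate.** Protocol 4.3 bases local tolerability on subjects who complete Induction. Section 3.3.3 reads this early reaction as possible pre-sensitization rather than irritation, and SAP 11.2.1 removes pre-photosensitized subjects from Population I for that product. This stands as a defence of the ANOVA set. It does not explain why a by-subject listing has to be restricted in the same way, and it does not square with the promise to summarize every score. SAP section 12 declares no departure from the protocol's analyses.

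**The tape asymmetry has a reason.** A reader might infer that the missing product exception is itself an error, since a tape withdrawal becomes an AE and a product withdrawal does not. The documents do not support that. Tape irritation is not graded at the patch site, so without an AE entry it would have no endpoint; product reactions are graded. The contradiction between 3.6.2.1 and the other two sections is a separate editorial matter.

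**The subject is not lost.** A reader might infer that the subject vanishes from the report. That is too strong. It is the reaction that is missing. The subject remains in the Population III denominator, counts for any other AE, and appears as a withdrawal. The scores stay on the CRF. An incomplete subject judged to demonstrate photosensitization can enter Population I and its sensitized count, although the table footnote ties that classification to Challenge and Rechallenge.

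**A second route is uncertain.** One might add subjects who reach the relocation limit: "Study product may not be relocated more than twice". Mandatory withdrawal at that limit is stated only in the tape paragraph, so the text does not establish it for product reactions.

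**Conclusion.** The point holds, and it is minor. On the explicit route in Protocol 3.3.3, a discontinuing product-site reaction is barred from the AE data and its scores reach no specified Induction table or listing. The cause is mainly a mismatch between the population headings on the SAP shells and the wider text of Protocol 4.6.1 and SAP 11.7.

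The gap depends on outcome, which is why it deserves correction, but its frequency is unknown. Discontinuation is at the investigator's discretion, and the number affected may be zero. The percentages above rest on assumed counts and are not forecasts.

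A reader might infer that the comparison of mean Induction scores or the photoallergy finding is compromised. The documents do not support this. The ANOVA is defined on completers and described in SAP 11.1 as supportive, and photosensitization is diagnosed by the investigator from Challenge and, where needed, Rechallenge.

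**What to change.** **Main change (SAP only).** Produce Listings 16.2.6.1 and 16.2.6.2 for all randomized subjects, as Listing 16.2.6.3 already is. Add a footnote to Tables 14.2.1.1 and 14.2.1.2 giving the number of treated subjects outside Population II who were discontinued for a product-site reaction, by product and irradiation status, with a pointer to the listing. The cost is two population headings and one footnote. No new data are needed, and the ANOVA and photosensitization results do not change. The listing also shows which site reacted, which the pooled AE table cannot do.

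**Optional change (protocol amendment).** Add one identical sentence to 3.6.1, 3.6.2.1 and 3.6.6, stating that a patch-site response leading to discontinuation of a product or of the subject is also recorded as an AE. It is then followed up under 3.6.4 and counted in Table 14.3.1.1. The tape sentence in 3.6.2.1 can be aligned with 3.6.6 at the same time. Under Protocol 5.5.1 this needs a written amendment approved by the sponsor and the principal investigator, and IRB approval if it significantly affects safety, scope or scientific quality. The downside is that a few reactions would appear both as scores and as AEs. All other scored responses stay out of the AE data.

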3.7. Instructions for Rapid Notification of Serious Adverse Events

3.7.1. Safety Contact person and number

Serious adverse events and pregnancies must be reported immediately (i.e., not later than 24 hours after first knowledge). The SAE or pregnancy report should be e-mailed or faxed to United BioSource Corporation (UBC) using the following e-mail or fax-number:

Email: [contact]

[contact]

3.7.2. Reporting Responsibility

Any death, SAE, pregnancy, (see [Section 3.6](#)), or unusual frequency of AEs, must be reported immediately (i.e., not later than 24 hours after first learning of its occurrence) to the Sponsor's study manager by the Investigator, even if the event(s) appear to be unrelated to study treatment. Follow-up information about a previously reported SAE or pregnancy must also be reported to the Sponsor within 24 hours of receiving it. If the SAE has not been previously documented (i.e., is a new occurrence) and it is thought to be related to the IP (or therapy), the Sponsor may contact the Investigator to obtain further information. If warranted, an investigator alert may be issued to inform all Investigators involved in any study with the same product (or therapy) that this SAE has been reported.

The IRB should also be notified of SAEs or pregnancies and of any follow-up information in writing, as is practical, and depending on local regulations.

